Potential benefits to subjects include the possibility of immediate mood improvement following LFMS. The need for immediate mood improving treatments in crisis and acute scenarios is important. The current delay between the start of anti-depressant therapy and the relief of symptoms is weeks, and is not effective in crisis situations. The discovery of a treatment with immediate effect would be an important addition to the treatment of depression. Additionally, current treatments for depression are not satisfactory for all patients, and any additional therapy alleviating symptoms would benefit patients and society. Finally, the response rate of patients to anti-depressant medication is low and the incidence of treatment resistance is high; this means that additional therapies are needed. The lack of demonstrated side effects from LFMS to date will allow widespread use, either as a monotherapy or as an adjunct therapy, without significant risks.

LFMS and Anxiety. In previous studies we found that LFMS affected symptoms of anxiety, in addition to depression. These results lead us to believe that LFMS should be explored for use in anxiety disorders. A detailed examination of the responses to the Hamilton Depression Rating Scale (HDRS) in the recent study shows that the largest effects are in the “psychic anxiety” and “somatic anxiety” items, along with “depressed mood” and “work and interest.” A similar examination of the Positive and Negative Affect Schedule (PANAS) results shows that the improvement is in many of the anxiety-related items on the negative scale such as “distressed,” “upset,” “scared,” “irritable” and “jittery” along with changes in many items on the positive scale such as “enthusiasm,” “pride” and “inspiration.” Based on this pattern of results, we propose that LFMS may offer relief from symptoms of depressed mood, anxiety, and irritability.

II. SPECIFIC AIMS (Research Objectives)

b. Specify objectives and hypotheses to be tested in the research project

Aim 1: To assess the safety and efficacy of regular LFMS in treating symptoms of depression in older adults suffering from bipolar depression.

- Hypothesis 1: We hypothesize that subjects will show long-term improvement in mood following the five days of LFMS experimental treatment, as measured by the Montgomery-Åsberg Depression Rating Scale (MADRS).

Aim 2: To assess the efficacy of regular LFMS in treating symptoms of anxiety in older adults suffering from bipolar depression.

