Clinical Global Impressions-Improvement Scale (CGI-I)			X	X	X	X	X	X	X	X
Clinical Global Impressions-Baseline		X								
Adverse Events Check-in		X	X	X	X	X	X	X	X	X

*Administered twice per visit, immediately before and immediately after LFMS treatment.

Safety Procedures

h. Suicidality Procedures

Suicidal ideation (SI) is not uncommon in people suffering from GBD. Suicidality will be assessed throughout the study during the screening visit, treatment visits and follow-up visits. Using the C-SSRS. The GPMADOC suicidality SOP will be prompted by over threshold responses for certain items on mood rating scales or by spontaneous report of suicidal ideation at any time. Specifically,

- The use of the GPMADOC Suicidality SOP will be triggered by spontaneous report of suicidal ideation or by over-threshold responses to specific items on mood ratings.
- The Suicidality SOP instructs the use of the C-SSRS and uses the responses to questions 4 and 5 as a threshold for physician involvement. If the responses to these two questions are “yes” then the study physician will be contacted for in-person assessment or for phone call-back assessment as appropriate. The C-SSRS will be completed while awaiting the physician.
- The following mood rating items and thresholds trigger use of the Suicidality SOP: C-SSRS, “yes” to questions 4 and 5; MINI, “yes” on items B7, B9 or B10; MADRS, 4 or 6 on item 10.

We note that the CGI is used for withdrawal criteria, but this scale is not used for suicidality assessment, but rather to ensure safe continuation of the study.

i. Medication or Therapy Changes

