At the phone screen and on site screening, potential subjects are informed that we do not ask them to discontinue their medications or treatments. However, we ask that they do not make changes to their medications or therapy prior to or during the experimental study period. Stable medication is not a confound. Subjects are also told that if their clinician believes it is in their best interest to make this change, they should do so. They will be asked to inform us if this is the case. We will not ask the subject to withdraw from the study, but their data will be excluded from analyses. If a subject withdraws from the study due to a change in medication, pregnancy or any other reason not related to the actual LFMS procedures and would like to return to the study in the future, they will be allowed to re-enroll. However, they must go through a 2 month washout period. The subject will be partially rescreened to confirm mood state and inclusion/exclusion criteria prior to their first treatment visit.

j. Study visits and parameters to be measured (e.g., laboratory tests, x-rays, and other testing)

Measures

Screening measures

- M.I.N.I International Neuro-Psychiatric Interview (MINI)
- Cumulative Illness Rating Scale – Geriatrics (CIRS-G)

Low Field Magnetic Stimulation: Initial Trial in Geriatric Bipolar Depression

- Montgomery Asberg Depression Rating Scale (MADRS)
- Mini Mental State Exam (MMSE)
- Hamilton Anxiety Rating Scale (HARS)
- Positive and Negative Affect Schedule (PANAS)
- LFMS Medical Screening Form
- LFMS Medications Form
- Clinical Global Impressions – Baseline (CGI-B)

Safety Measures

- Columbia Suicide Severity Rating Scale (C-SSRS)
- Clinical Global Impressions – Improvement Scale (CGI-I)

Long-term measures

- Montgomery-Åsberg Depression Rating Scale (MADRS)
- Hamilton Anxiety Rating Scale (HARS)
- Repeatable Battery for the Assessment of Neuropsychological Status (RBANS)
- Young Mania Rating Scale (YMRS)

Short-term measures

- Positive and Negative Affect Schedule (PANAS)

Screening (Visit 1) Procedures

A study staff member will obtain informed consent (see consent procedures above IV.b.). If informed consent is obtained, then the screening procedures will proceed.

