During the screening visit, a trained clinical study staff member will interview and assess the subject using the Screening Measures, during which a detailed medical history will be obtained and current medications noted. Suicidality risk is assessed as part of the Safety Measures; a positive response to items 4 or 5 of the C-SSRS will prompt the use of the Suicidality SOP.

A urine drug screen and, if female, a pregnancy test will be performed. Subjects will be accepted for the treatment trial based on the interview and review of results by a study physician.

The screening visit, including the rating scales and physical exam, will take approximately 2 hours and will be done up to one week before the baseline visit. If subjects meet study criteria after the screening visit, a baseline visit will be scheduled.

Baseline (Visit 2) Procedures

Contingent on a successful screening visit, subjects will come in for a baseline visit on the Thursday or Friday prior to the 5 days of consecutive LFMS treatment. This visit will take about 1 hour to complete. Subjects will be administered Long- and Short-Term mood scales as well as the Safety Measures. A positive response to items 4 or 5 on the C-SSRS will prompt the use of the Suicidality SOP (see ‘Suicidality Procedures’ above).

LFMS (Visits 3-7) Procedures

Subjects will come in for 5 daily consecutive LFMS treatments over a period of five days, Monday-Friday. If subjects are unable to come in for five consecutive days due to a scheduling conflict, we will accept a schedule of four consecutive days without considering this a protocol deviation. Women of childbearing potential will be required to complete a urine pregnancy screen at screening and before each LFMS procedure.

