The Safety Measures will be administered. As part of these, the C-SSRS will be used as a suicidality risk assessment and any positive response to items 4 or 5 will prompt the use of the Suicidality SOP (see ‘Suicidality Procedures’ above). The second part of the Safety Measures is the CGI-I, which will be used to ensure safe continuation of the study; a score of 6 or more will prompt a consultation with the study physician and potential withdrawal from the study (see “Withdrawal Criteria” above). Medication and/or treatment changes will be asked about and noted. Changes in treatment will not prompt withdrawal but will indicate that data will be excluded from analysis (see “Medication and Therapy Change Procedures” above). A brief progress note will be recorded. The Short- and Long-Term mood scales will be

Low Field Magnetic Stimulation: Initial Trial in Geriatric Bipolar Depression

administered, and LFMS procedures will begin immediately after these mood ratings are completed. HARS and MADRS Long-Term mood scales will only be administered on Visits 3, 5, and 7.

Randomization occurs automatically when the subject number is entered on the LFMS Device during the first treatment visit.

For LFMS procedures, the subject will lie down on the patient table with his/her head positioned inside the device cylinder, and the operator will start the LFMS device. The device has been designed so that the cylinder does not extend below the eyes in order to reduce claustrophobia. Subjects will be instructed to remain silent during the treatment, except in cases of discomfort, desire to discontinue treatment, or similar situations related to subject safety and study participation. Subjects will be given one 20 minute exposure to either the LFMS or sham electromagnetic field treatment. Subjects will be told they may receive either the active treatment or a sham, inactive treatment.

After treatment, the Short-Term Measures will be completed again to obtain post-treatment scores. Subjects will also be asked about possible side effects or sensations. After the treatment and mood ratings, subjects may leave immediately or rest in the Imaging Center waiting area until they are ready to leave or return to the GPMADOC and the SAGE Program, located in South Belknap.

Follow-up Visit (Visit 8)

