During the treatment visits, research data will be obtained through mood rating scales before and after the LFMS procedures, and through self-report from the subjects. Research data will also be obtained from subjects through mood rating scales at the follow-up visits, one week after the start of the set of 5 experimental LFMS procedures.

VI. BIOSTATISTICAL ANALYSIS

d. Specific data variables being collected for the study (e.g., data collection sheets).

The primary long-term measures will be the change in MADRS and HARS scores at one week compared to baseline across the treatment week. This analysis will be a repeated measures ANOVA with a baseline covariate. The primary short-term analyses using the PANAS scores, which provide additional insight into the details of mood change, will be performed in the same way.

e. Study endpoints

The main endpoint of this study is that participants will well tolerate 5 daily active treatments. A secondary endpoint is the expectation that participants will experience a persistent increase in positive mood at one week after the start of treatment. Change in mood over the first treatment is an additional measure that will ensure comparability of the study to previous studies.

f. Statistical methods and Power analysis

This is an exploratory study being performed to characterize the effects of LFMS over daily treatments and at one week in a target population. As the endpoints are safety and tolerance by the participants, no power analysis has been performed. We expect to be able to make the first estimate of an effect size based on the results of this study.

VII. RISKS AND DISCOMFORTS (Stratify by common and uncommon)

d. Complications of surgical and non-surgical procedures, etc.

Risks Related to Confidentiality and Privacy

There is a risk that a breach of privacy or confidentiality could occur. But, all study staff are trained in how to preserve confidentiality and privacy. Risks will be minimized by storing subject data and personal information on a password protected computer or in a locked filing cabinet in a locked office, accessible only to study staff.

Psychosocial (non-medical) risks

There is a risk that questions during the treatment visits about mental health and mood state may upset the subject psychologically. Subjects are free to take a break from or to stop answering these questions at any time, and a study physician will be able to assist them if needed.

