Due to the nature of affective disorders, it is possible that a subject may develop or experience an increase in suicidal ideation during their participation in the study. If it is determined that a subject has developed increased suicidal thinking, either through increased scores on the or through conversation with clinical study staff, a study physician and the subject's clinician will be called immediately.

e. Drug side effects and toxicities

N/A

f. Device complications/malfunctions

Risks Related to LFMS Device

LFMS technology does not use ionizing radiation. Instead, it uses electric field pulses that may stimulate the brain. There are no known hazards or risks associated with this technique. The LFMS device, unlike an MR scanner, has no permanent magnet and thus has no magnetic field when not in active operation. During treatment there is a small, low frequency magnetic field near the device. This field is less than 5 Gauss when further than 1.5 feet from the device. We plan to be conservative and follow the 5 Gauss guidelines for MRI sites and place a magnetic area sign in the doorway during treatment sessions, to warn anyone who may enter the room during the 20 minute treatment. Outside of the treatment time, there are no fields and thus no safety issues.

Persons with pacemakers, neurostimulators, or metal in head or neck will not be enrolled or allowed in the room during device operation.

Low Field Magnetic Stimulation: Initial Trial in Geriatric Bipolar Depression

There is a red button on the device that can be manually pushed in the event of a hardware failure or an emergency. This mechanically disconnects the coil from the power source and dumps the energy stored in the coil safely to a heat dissipative resistor. If the subject asks to terminate the experiment or experiences a medical emergency, there is a “stop” button on the interface that can be clicked with the computer mouse, and this will stop waveform execution.

Risks Related to Pregnancy

There are no known risks for pregnancy associated with this type of electromagnetic field exposure. However, in order to ensure subject safety, women who are pregnant, as confirmed by pregnancy test, will be excluded from this study.

Radiation Risks (statement provided by Radiation Safety Committee)

N/A

VIII. POTENTIAL BENEFITS

b. Potential benefits to participating individuals and/or to society

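### The rule that excludes data after a medication or therapy change makes no exception for safety data, and the C-SSRS trigger for physician contact is worded in two conflicting ways

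*Combined protocol and SAP*

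**What the plan says.** The Medication or Therapy Changes section (Phase 1 V.b, Phase 2 V.i) asks subjects to keep treatment constant but tells them that "if their clinician believes it is in their best interest to make this change, they should do so". The consequence is: "We will not ask the subject to withdraw from the study, but their data will be excluded from analyses". The treatment-visit and follow-up-visit procedures of both phases repeat it: "Changes in treatment will not prompt withdrawal but will indicate that data will be excluded from analysis". There it stands in the same paragraph as the Safety Measures. No statement of the rule says which outcomes or analyses it covers.

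Aim 1 in both phases is "To assess the safety and efficacy of regular LFMS in treating symptoms of depression in older adults suffering from bipolar depression". Section VI makes tolerability of the daily active sessions the main endpoint and adds: "As the endpoints are safety and tolerance by the participants, no power analysis has been performed". The analyses it describes are repeated-measures ANOVA of MADRS and HARS, with BDI and BAI in Phase 1 (PANAS-X exploratory) and PANAS in Phase 2. The C-SSRS is rated at all nine Phase 1 visits and all ten Phase 2 contacts. No summary by arm of the C-SSRS, CGI-I, adverse events or tolerability is described.

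Under psychosocial risks (Section VII), if suicidal thinking is found to have increased, "a study physician and the subject's clinician will be called immediately".

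On the threshold, the Suicidality Procedures (Phase 1 V.a, Phase 2 V.h) say that the SOP "uses the responses to questions 4 and 5 as a threshold for physician involvement". They make physician contact conditional on a yes to both, and their list of SOP triggers uses the same 'and'. The screening procedures say instead that "a positive response to items 4 or 5 of the C-SSRS will prompt the use of the Suicidality SOP". The treatment-visit, follow-up-visit and (Phase 2) phone-call procedures likewise act on either item.

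**The concern.** A change of treatment happens after randomisation and can be a response to how the subject is doing. If subjects are left out of a safety summary for that reason, those left out may be the ones who got worse. Any tolerability statement would then rest on a set partly selected on the outcome it describes. Because the plan defines neither a safety summary nor its population, the unqualified exclusion rule is the only express written rule on whose data count.

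The threshold mismatch is a matter of procedure rather than analysis. A subject positive on only one of the two questions would start the SOP under the visit procedures but would not meet the SOP's stated condition for physician contact.

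**Working it through.** The plan gives no power, event rate or effect size, so there is no figure to reproduce. The check is mainly one of text.

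**1. Scope of the rule.** The rule appears in the Medication or Therapy Changes section, the treatment-visit procedures and the follow-up-visit procedures of each phase. None of these limits it to efficacy or exempts the C-SSRS, CGI-I or adverse events. Section VI does not narrow it.

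**2. From worsening to exclusion.**
- Increased suicidal thinking leads to a call to the subject's clinician: stated (Section VII).
- A change the clinician judges best should be made: stated (V.b, V.i).
- A change leads to exclusion of data: stated (V.b, V.i).
- The call leads to a change: not stated. This step is an inference.

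**3. Illustration of size.** Phase 2 targets 32 completers (Section III) in two equal groups (IV.f), so 32/2 = 16 per arm. Assume that 2 of 16 active subjects worsen and that k of those 2 have treatment changed. No one else changes treatment. The rule then leaves (2 − k)/(16 − k):

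| k | Reported | Proportion |
|---|---|---|
| 0 | 2/16 | 12.5% (exact 95% CI 1.6% to 38.3%) |
| 1 | 1/15 | 6.7% |
| 2 | 0/14 | 0% (upper limit 1 − 0.025^(1/14) = 23.2%) |

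If 1 or 3 subjects worsen and all of them have treatment changed, 1/16 (6.3%) becomes 0/15 and 3/16 (18.8%) becomes 0/13.

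**4. Direction.** Let p be the true proportion who worsen, a the chance of a treatment change in those who worsen, and b the chance in the others. The expected reported proportion is about

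p(1 − a) / [p(1 − a) + (1 − p)(1 − b)].

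If a = b this returns p, so there is no bias. If a > b it understates p. The documents give none of p, a or b.

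**5. C-SSRS threshold.**

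| Yes to | SOP starts (visit procedures) | SOP starts (C-SSRS trigger in V.a, V.h) | Physician contact (V.a, V.h) |
|---|---|---|---|
| 4 only | yes | no | no |
| 5 only | yes | no | no |
| both | yes | yes | yes |

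The two wordings agree only when both answers are yes (or both no).

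**The case against.** The strongest reply is that the rule was meant for efficacy only. The same section explains that unchanged medication does not confound, which is a concern about mood outcomes, and the only analyses in Section VI are of mood scales. Adverse-event monitoring and reporting sit in Section IX, with monthly review and reporting to the IRB/PHRC, and are not made subject to the rule. This reading is plausible and may be what was intended, but the text does not say so. Case reporting is also not a comparison with sham.

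Second, no C-SSRS summary is planned, so the rule removes nothing from a table that exists. That stands: the more basic gap is that the declared endpoint has no described analysis. The rule matters once a summary is written.

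Third, the most serious cases may leave by another route, since dangerous or active suicidal ideation is a withdrawal criterion. That also stands, but the plan does not say whether ratings taken before removal are kept.

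A reader might infer that suicidality events will be hidden, or that reports of zero events can be shown to become more likely by a known amount. The documents do not support either. The step from suicidality to a treatment change is inferred, and any event rate or change rate would be an assumption. Nor do they show that the safety set would be chosen after unblinding, since nothing prevents it from being fixed while blinded. The rule also does not impair detection or care, because the ratings, the SOP and case reporting continue regardless.

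On the threshold, there are partial backstops: the Section VII instruction, the physician consultation at a CGI-I score of 6 or more, and the other SOP triggers. The SOP itself is only summarised here. None of these resolves the conflict in wording.

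**Conclusion.** The point holds as a gap in wording that should be closed. Both phases exclude data after a treatment change without qualification, while safety and tolerance are the declared endpoints. Taken literally, the rule would apply to any safety summary, and exclusion could depend on the outcome.

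Harm is possible but not shown. It requires that 'analyses' include safety, that a safety summary be produced, and that treatment changes be more common in subjects who worsen. Its size cannot be derived from the documents. The fall from 2/16 to 0/14 is an illustration with assumed counts. It uses 16 completers per arm as the denominator, whereas a set of all treated subjects may be larger. At this size a by-arm table is descriptive and cannot establish or rule out a device effect. The issue does not invalidate the trial.

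The 'and'/'or' conflict over C-SSRS questions 4 and 5 is a definite inconsistency in both phases and rests on no assumption.

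**What to change.** 1. In the Medication or Therapy Changes section and in Section VI of both phases, state that the exclusion does not apply to safety and tolerability data: C-SSRS, CGI-I and adverse events. If efficacy alone was intended, this sentence confirms it.
2. Define the safety set as every subject who received at least one session, including data collected before removal or withdrawal.
3. Report these outcomes descriptively, by arm in Phase 2 and by condition and period in Phase 1, and flag subjects whose medication or therapy changed.
4. Separately, in the Suicidality Procedures (Phase 1 V.a, Phase 2 V.h), change 'and' to 'or' for questions 4 and 5, both for the SOP trigger and for physician contact, so that a subject positive on one item reaches a physician.

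The cost is a few sentences, one small descriptive table per phase, and possibly a few more physician contacts. No new visits or assessments are needed.

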programs will identify patients from their group that may be potential subjects. We have also obtained permission from the clinical directors of these programs to have a research coordinator look through electronic patient charts using Epic to identify eligible subjects. Once a potential subject has been identified, study staff will discuss the possibility of study participation with the patient's doctor and/or case manager to determine if the study would be appropriate. Potential subjects may be given an informational flyer about the study by clinical staff. The clinicians and staff members will not discuss aspects of the study with potential subjects so as to prevent the patient from experiencing undue pressure from their provider. We expect that potential subjects may be confused and/or upset if they were contacted by research staff at McLean without prior knowledge. Therefore, involving clinical staff as the first point of contact is essential to bridge patient communication between the two institutions. Clinicians will not be required or pressured to enroll patients in the study and patients' routine clinical care will not be jeopardized in any way if they choose not to participate. Potential subjects will be told that participation is completely voluntary and can be terminated at any time, for any reason by the patient.

A clinical research study staff member will contact interested and viable study candidates to explain the study procedures, answer any questions that the potential subject may have and conduct a pre-screening interview over the phone. Pre-screen interviews will be reviewed with the principal investigator on a weekly basis. Potential subjects who pass the pre-screen interview and are still interested in the study will be scheduled for an informed consent and prescreening visit at McLean Hospital.

Acceptance will rely on approval by one of the study physicians, in addition to satisfying all other criteria.

Subjects will be paid \$30.00 for each visit (not including phone follow-ups) to help cover the cost of travel and meals. Subjects may earn a maximum of \$240.00 over the course of the 8 visits.

IV. SUBJECT ENROLLMENT

d. Methods of enrollment, including procedures for patient registration and/or randomization

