Subjects will be distributed equally into two groups. One group will receive active LFMS during the treatment week and the other group will receive sham LFMS during the treatment week. Treatment assignments will be randomized and balanced within blocks of 10. Randomization is performed automatically on the first treatment visit. The LFMS Device contains a pre-randomized folder of subject treatment links that are assigned to subjects as they arrive for their first treatment. This list was randomized in ten-subject blocks at the start of the study (using a random number generator). This randomization schedule has since been updated to reflect the parallel-group, 5-day design of this protocol.

V. STUDY PROCEDURES

Study Overview

b. Study visits and parameters to be measured (e.g., laboratory tests, x-rays, and other testing)

This study will consist of a screening visit; a baseline visit; we will aim to administer four or five daily LFMS treatment or sham treatment visits over a period of five days and one in-person follow-up visit for ratings on the Monday after the treatment week. If a subject is unable to attend only one treatment visit in the five day window, this will not be considered a protocol violation. Follow-up rating scales will be administered by phone once per week for two weeks following the last visit.

Visits and Procedures	Screening	Baseline	LFMS experimental treatment					Follow-Up Visit	Follow-Up Phone Call	Follow-Up Phone Call
	Visit 1	Visit 2	Visit 3	Visit 4	Visit 5	Visit 6	Visit 7	Visit 8		
LFMS			X	X	X	X	X			
M.I.N.I International Neuro-Psychiatric Interview (MINI)	X									
Cumulative Illness Rating Scale (CIRS-G)	X									
Mini-Mental State Exam	X									
Repeatable Battery for the Assessment of Neuropsychological Status (RBANS)		X						X		
LFMS Demographics Form	X									
LFMS Medical Screening Form	X									
LFMS Medications Form	X									
Drug Test	X									
Pregnancy Test	X		X	X	X	X	X			
Montgomery-Asberg Rating Scale (MADRS)	X	X	X		X		X	X	X	X
Hamilton Anxiety Rating Scale (HARS)		X	X		X		X	X	X	X
Positive and Negative Affect Schedule (PANAS)*		X	X	X	X	X	X	X	X	X
Young Mania Rating Scale (YMRS)	X	X	X	X	X	X	X	X	X	X

Low Field Magnetic Stimulation: Initial Trial in Geriatric Bipolar Depression

Columbia Suicide Severity Rating Scale (C-SSRS)	X	X	X	X	X	X	X	X	X	X

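### Phase 2 rates manic symptoms at all ten contacts, but no endpoint or analysis uses the scores, so the plan has no pre-specified way to report them by arm

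*Combined protocol and SAP*

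**What the plan says.** All references are to Phase 2 of the protocol; Phase 1 schedules no mania scale.

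- **Purpose.** Aim 1 (Section II.b) is "To assess the safety and efficacy of regular LFMS in treating symptoms of depression in older adults suffering from bipolar depression". Section VI.f gives no power analysis, with the reason "As the endpoints are safety and tolerance by the participants".
- **Schedule.** The table in Section V.b marks the "Young Mania Rating Scale (YMRS") in every column: screening, baseline, treatment Visits 3 to 7, Visit 8 and both phone calls.
- **Filing.** Section V.j lists the YMRS under Long-term measures, with MADRS, HARS and RBANS. The Safety Measures list has two entries, the C-SSRS and the "Clinical Global Impressions – Improvement Scale (CGI-I"). The procedures for Visits 3-7 agree: "The second part of the Safety Measures is the CGI-I, which will be used to ensure safe continuation of the study".
- **Analysis.** Section VI.d states: "The primary long-term measures will be the change in MADRS and HARS scores at one week compared to baseline across the treatment week". It adds PANAS for the short term. Section VI.e makes tolerance of five daily active treatments the main endpoint, without naming a scale or a definition, and positive mood at one week a secondary endpoint.
- **Treatment changes.** Section V.i, repeated in the procedures for Visits 3-7 and Visit 8, keeps a subject whose medication or therapy changes in the study but excludes that subject's data from analysis. No exception is made for safety data.

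**The concern.** All subjects have Bipolar I or II disorder, and the device is studied because it is thought to raise mood. Whether it also raises manic symptoms is a direct safety question, and the trial collects the scale that addresses it. The schedule suggests a safety purpose: on treatment days MADRS and HARS are rated only at Visits 3, 5 and 7, while the YMRS is rated at every contact, as the C-SSRS is.

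The secondary endpoint counts an increase in positive mood as benefit. With no planned look at the YMRS beside it, Section VI cannot separate antidepressant benefit from movement toward mania. A report could follow the plan to the letter and conclude that treatment was well tolerated without showing manic symptoms by arm. The exclusion rule adds to this, because the subjects in whom a switch led to a change of treatment are those whose data the plan removes.

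**Working it through.** The plan states no sample-size or power figure, so there is none to reproduce. The check has three parts.

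**1. Number of ratings.**
- In-person visits: Section III.f pays 30 dollars per visit and says "Subjects may earn a maximum of \$240.00 over the course of the 8 visits"; 240 / 30 = 8.
- Phone contacts: "Follow-up rating scales will be administered by phone once per week for two weeks following the last visit", so 2.
- Contacts with a YMRS rating: 8 + 2 = 10, matching the ten marks in the table.
- Ratings before any exposure: screening, baseline and Visit 3, because on treatment days the long-term scales precede LFMS and only the short-term measures are repeated afterwards. That is 3.
- Ratings after first exposure: 10 − 3 = 7 (Visits 4 to 8 and two calls).
- In the 32 target completers (Section III): up to 7 × 32 = 224. If every subject followed the permitted four-treatment schedule and the missed visit was not rated: 6 × 32 = 192.

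**2. Planned uses of the YMRS.**

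| Place in the plan | What it uses | YMRS? |
|---|---|---|
| Hypotheses 1-3 (II) | MADRS, HARS, RBANS | No |
| Withdrawal criteria (III.e) | Eligibility, suicidality, CGI-I, discomfort | No |
| Safety Measures (V.j) | C-SSRS, CGI-I | No |
| Analysis variables (VI.d) | MADRS, HARS, PANAS | No |
| Endpoints (VI.e) | Tolerance, positive mood, change over first treatment | No |

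**3. What a by-arm report could show.** Assume the 32 completers split equally, 16 per arm.
- Zero switches on active: one-sided 95% upper bound 1 − 0.05^(1/16) = 17.1%; two-sided exact upper bound 1 − 0.025^(1/16) = 20.6%.
- Chance of at least one switch among 16, 1 − (1 − p)^16, for assumed true rates p (the documents give none):

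| Assumed rate | 2% | 5% | 10% | 15% |
|---|---|---|---|---|
| Chance of at least one | 27.6% | 56.0% | 81.5% | 92.6% |

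- Against 0 of 16 on sham, Fisher's exact two-sided p is 0.101 for 4 of 16 on active and 0.043 for 5 of 16. Five switches would be needed to pass 0.05.
- A rise of R points in one active subject moves that arm's mean by only R/16, about 6% of R. A comparison of means can therefore hide a single switch, so individual maxima have to be listed as well.

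**The case against.** The strongest reply is that a switch would not go unseen. The schedule has an adverse-event check-in at every contact from baseline to the last call. Side effects are asked about after each treatment. A CGI-I score of 6 or more prompts a physician consultation, and Section IX.d provides for monitoring of mood assessments. This stands. A reader might infer that the trial would miss mood switching altogether, and the documents do not support that. But none of these routes names mania, uses the YMRS scores or leads to a comparison by arm.

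Three other inferences also go too far.
- **That the scores will never be used.** Section VI.d describes primary measures and need not be exhaustive; RBANS has its own hypothesis and is also absent there. What can be said is that no use is pre-specified.
- **That filing under Long-term measures is the cause.** The C-SSRS and CGI-I are on the Safety Measures list, and Section VI analyses neither. Moving the YMRS would not create an analysis. That list is also operational, since its items lead to the suicidality procedure, physician consultation or possible withdrawal, so adding to it is a clinical matter.
- **That all 10 × 32 = 320 ratings bear on treatment, or that the 17.1% bound shows how much the YMRS would add.** Three ratings per subject precede exposure. The bound concerns event counts in 16 completers and says nothing about YMRS precision; the documents give no YMRS standard deviation.

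The study is declared exploratory. That is a reason for a descriptive analysis, but not for leaving a safety scale without one when safety is the stated endpoint.

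**Conclusion.** The point holds as a gap in planned reporting. Phase 2 rates the YMRS at ten contacts, seven after first exposure, up to 224 ratings in 32 completers, and no endpoint or analysis uses them. A conclusion on tolerability would then rest on non-specific routes for manic symptoms, and the exclusion rule could remove subjects treated for such symptoms. How many that might be cannot be estimated from the documents.

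The counts assume full attendance by completers, and the 16 per arm assumes an equal split; the set of all treated subjects may be larger, since up to 64 may be enrolled. Nothing here shows that LFMS raises manic symptoms, and a trial of this size could not exclude it. The change should be made, but it does not affect the design.

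**What to change.** Add to Section VI, before unblinding:

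1. Name the YMRS as a safety outcome.
2. Define the set as all treated subjects, including those whose medication or therapy changed, and state that the exclusion rule in Section V.i does not apply to it.
3. Fix the baseline in advance: Visit 2, or Visit 3 before LFMS.
4. List each subject's maximum rise from that baseline over Visits 4-8 and the two phone calls, with the number of ratings available and any treatment change, and summarise the maxima by arm.
5. Give the active-versus-sham difference in baseline-adjusted YMRS change with a confidence interval, labelled descriptive and not as a test that rules out switching.

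Separately, reconcile the schedule table, which marks the YMRS at screening, with the Screening measures list in Section V.j, which omits it. The content of the Safety Measures list, and any YMRS threshold or action, are for the investigators; none is proposed here.

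The cost is one listing, one summary table and one model on data already scheduled, with no new visit or procedure.
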